12.1.3 Non-serious adverse event

A non-serious AE is any AE which does not fulfil the definition of an SAE.

12.1.4 Medication errors

A medication error concerning trial products is defined as:

- Administration of wrong drug.
 Note: Use of wrong dispensing unit number (DUN) is not considered a medication error unless it results in administration of wrong drug.
- Wrong route of administration,
- Administration of an overdose with the intention to cause harm (e.g. suicide attempt), misuse or abuse of trial product.
- Accidental administration of a lower or higher dose than intended. However, the administered dose must deviate from the intended dose to an extent where clinical consequences for the trial patient were likely to happen as judged by the investigator, although they did not necessarily occur

Medication errors must be reported on an AE form and a specific event form, see Section [8.4.5.1](#)

Protocol
 Trial ID: NN7415-4255
 UTN: U1111-1179-3872
 EudraCT no.: 2016-000614-29

~~CONFIDENTIAL~~

Date: 28 December 2017
 Version: 4.0
 Status: Final
 Page: 81 of 124

Novo Nordisk

12.1.5 Adverse events requiring additional data collection

AEs requiring additional data collection are AEs where the additional data will benefit the evaluation of the safety of the trial product.

In this trial the following AEs require the completion of specific event forms in the eCRF:

- Injection site reaction (see section [8.4.5.2](#))
- Hypersensitivity type reactions, incl. anaphylactic reactions, as defined below

Injection site reactions:

Any injection site reaction symptom must be reported on the AE form and the injection site reaction form, See section [8.4.5.2](#).

Hypersensitivity type reactions:

In cases where clinical signs of a severe and immediate hypersensitivity reaction resembling a type I hypersensitivity reaction are present, blood should be sampled for central laboratory assessment of anti-drug IgE antibodies and anti-drug binding antibodies. In the event of an immediate systemic hypersensitivity reaction to the trial product, it is recommended to also test for tryptase (total and/or mature tryptase) within 3 hours of the reaction. Moreover, a baseline tryptase measurement is necessary ~1 week after the immediate severe hypersensitivity reaction due to individual to individual variation in tryptase baseline concentration. Tryptase concentrations (if measured) must be interpreted and considered in the context of a complete workup of each patient.

Special attention should be given to clinical signs and symptoms of hypersensitivity reactions of type II and III. Common clinical signs and symptoms characteristic for these types of reactions may include but are not limited to: fever/malaise, cutaneous eruptions, arthralgia, lymphadenopathy, itching, headaches and myalgia. Related laboratory findings may include but are not limited to: mild proteinuria or haematuria, leukopenia or leucocytosis, decreased complement levels or increased complement split products and transient elevations of serum creatinine levels. In cases where there is a suspicion of hypersensitivity reaction that requires systemic treatment, additional sampling for the purpose of measuring ADA is to be performed.

Definition of anaphylaxis²³

Anaphylaxis is highly likely when **any one of the following 3 criteria** is fulfilled:

- Acute onset of an illness (minutes to several hours) with involvement of the skin, mucosal tissue, or both (e.g. generalised hives, pruritus or flushing, swollen lips-tongue-uvula) **and at least one of the following:**
 - a) Respiratory compromise (e.g. dyspnoea, wheeze-bronchospasm, stridor, reduced peak expiratory flow [PEF], hypoxemia)
 - b) Reduced blood pressure (BP) or associated symptoms of end-organ dysfunction (e.g. hypotonia [collapse], syncope, incontinence)

Protocol
 Trial ID:NN7415-4255
 UTN:U1111-1179-3872
 EudraCT no.:2016-000614-29

~~CONFIDENTIAL~~

Date:	28 December 2017	Novo Nordisk
Version:	4.0	
Status:	Final	
Page:	82 of 124	

- **Two or more of the following** that occur rapidly after exposure to a likely allergen for that patient (minutes to several hours):
 - a) Involvement of the skin-mucosal tissue (e.g. generalised hives, itch-flush, swollen lips-tongue-uvula)
 - b) Respiratory compromise (e.g. dyspnoea, wheeze-bronchospasm, stridor, reduced PEF, hypoxemia)
 - c) Reduced BP or associated symptoms (e.g. hypotonia [collapse], syncope, incontinence)
 - d) Persistent gastrointestinal symptoms (e.g. crampy abdominal pain, vomiting)
- Reduced BP after exposure to known allergen for that patient (minutes to several hours): Systolic BP of less than 90 mm Hg or greater than 30% decrease from that person's baseline BP.

If a patient fulfils any of the three criteria of anaphylaxis outlined above, the patient should receive epinephrine/adrenalin immediately. Dose regimen should be according to hospital operating procedure, and the patient should be transferred to an emergency department or intensive care unit, if clinically warranted.

Events not fulfilling the criteria for an anaphylactic reaction and other allergic reactions must be treated at the discretion of the investigator. If according to the investigators judgment, hypersensitivity type reactions that require systemic treatment are suspected, dosing with concizumab should be stopped immediately and treatment at the discretion of the treating physician initiated.

12.1.6 Adverse event of special interest

An adverse event of special interest (AESI) is an event, which in the evaluation of safety, has a special focus. In this trial, the following AEs fulfil the AESI criteria:

- Thromboembolic events including but not limited to,
 - disseminated intravascular coagulation (DIC) (A),
 - clinical signs or laboratory indications of arterial and venous thrombosis including myocardial infarction (B),
 - pulmonary embolism (C),
 - stroke (D),
 - deep vein thrombosis (E),
 - other clinically significant thromboembolic events (F) and peripheral artery occlusion (see below G), see definitions below.

The AESIs must be reported on an AE form and a safety information form.

Protocol
 Trial ID:NN7415-4255
 UTN:U1111-1179-3872
 EudraCT no.:2016-000614-29

~~CONFIDENTIAL~~

Date:	28 December 2017	Novo Nordisk
Version:	4.0	
Status:	Final	
Page:	83 of 124	

A) Definition of disseminated intravascular coagulation (DIC), as defined below:

The definition of DIC in this trial should be made according to the International Society on Thrombosis and Haemostasis (ISTH) criteria. Thus, a DIC diagnosis may be based on clinical signs and symptoms of a bleeding tendency or thrombotic tendency, organ dysfunction and the laboratory parameters criteria as listed below:

- Platelet count ($>100 \times 10^9/L = 0$, $<100 \times 10^9/L = 1$, $<50 \times 10^9/L = 2$)
- Elevated D-dimer (no increase = 0, moderate increase = 2, strong increase = 3)
- Prolonged PT ($<3 \text{ s} = 0$, $>3 \text{ but } <6 \text{ s} = 1$, $>6 \text{ s} = 2$)
- Fibrinogen level ($>1 \text{ g/L} = 0$, $<1 \text{ g/L} = 1$)
- Calculate score: ≥ 5 compatible with overt DIC

(B) Myocardial infarction is defined according to the “Third Universal Definition of Myocardial Infarction”²⁴

Criteria for acute myocardial infarction - The term acute myocardial infarction (MI) should be used when there is evidence of myocardial necrosis in a clinical setting consistent with acute myocardial ischemia. Under these conditions any one of the following criteria meets the diagnosis for MI:

- Detection of a rise and/or fall of cardiac biomarker values [preferably cardiac troponin (cTn)] with at least one value above the 99th percentile upper reference limit (URL) and with at least one of the following:
 - Symptoms of ischemia.
 - New or presumed new significant ST-segment–T wave (ST–T) changes or new left bundle branch block (LBBB).
 - Development of pathological Q waves in the ECG.
 - Imaging evidence of new loss of viable myocardium or new regional wall motion abnormality.
 - Identification of an intracoronary thrombus by angiography or autopsy.

Criteria for prior myocardial infarction- Any one of the following criteria meets the diagnosis for prior MI:

- Pathological Q waves with or without symptoms in the absence of non-ischemic causes. Imaging evidence of a region of loss of viable myocardium that is thinned and fails to contract, in the absence of a non-ischemic cause.
- Pathological findings of a prior MI.

Recurrent myocardial infarction - Incident MI' is defined as the individual's first MI. When features of MI occur in the first 28 days after an incident event, this is not counted as a new event for epidemiological purposes. If characteristics of MI occur after 28 days following an incident MI, it is considered to be a recurrent MI.

C) Definition of pulmonary embolism:

Protocol
 Trial ID: NN7415-4255
 UTN: U1111-1179-3872
 EudraCT no.: 2016-000614-29

~~CONFIDENTIAL~~

Date:	28 December 2017	Novo Nordisk
Version:	4.0	
Status:	Final	
Page:	84 of 124	

The “Clinical Practice Guideline from the American Academy of Family Physicians and the American College of Physicians” on diagnosis of venous thromboembolism recommends diagnostic imaging studies for patients with intermediate or high pre-test probability of pulmonary embolism²⁵.

Accordingly, the definition of pulmonary embolism is the following: obstruction of a pulmonary artery or one of its branches, most frequently by detached fragments of thrombus from a leg or pelvic vein, diagnosed by at least one of the following:

- Positive findings in ventilation/perfusion scan
- Positive findings in a spiral (helical) computerised tomography (CT) or angiography
- Positive findings in a magnetic resonance imaging (MRI)
- Positive findings in a pulmonary angiography

D) Definition of stroke:

The definition of central nervous infarction is according to the American Heart Association/American Stroke Association Expert Consensus Document: “An Updated Definition of Stroke for the 21st Century”²⁶.

Accordingly, the term “stroke” should be broadly used to include all of the following:

Definition of central nervous system (CNS) infarction: CNS infarction is brain, spinal cord, or retinal cell death attributable to ischemia, based on:

- 1. pathological, imaging, or other objective evidence of cerebral, spinal cord, or retinal focal ischemic injury in a defined vascular distribution; or
- 2. clinical evidence of cerebral, spinal cord, or retinal focal ischemic injury based on symptoms persisting 24 hours or until death, and other etiologies excluded.

Note: CNS infarction includes haemorrhagic infarctions, types I and II; see “Haemorrhagic Infarction”.

Definition of ischemic stroke: An episode of neurological dysfunction caused by focal cerebral, spinal, or retinal infarction. Note: Evidence of CNS infarction is defined above.

Definition of silent CNS infarction: Imaging or neuropathological evidence of CNS infarction, without a history of acute neurological dysfunction attributable to the lesion.

Definition of intracerebral haemorrhage: A focal collection of blood within the brain parenchyma or ventricular system that is not caused by trauma. Note: Intracerebral haemorrhage includes parenchymal haemorrhages after CNS infarction, types I and II - see “Haemorrhagic Infarction”.

Definition of stroke caused by intracerebral haemorrhage: Rapidly developing clinical signs of neurological dysfunction attributable to a focal collection of blood within the brain parenchyma or ventricular system that is not caused by trauma.

Protocol
 Trial ID:NN7415-4255
 UTN:U1111-1179-3872
 EudraCT no.:2016-000614-29

~~CONFIDENTIAL~~

Date:	28 December 2017	Novo Nordisk
Version:	4.0	
Status:	Final	
Page:	85 of 124	

Definition of silent cerebral haemorrhage: A focal collection of chronic blood products within the brain parenchyma, subarachnoid space, or ventricular system on neuroimaging or neuropathological examination that is not caused by trauma and without a history of acute neurological dysfunction attributable to the lesion.

Definition of subarachnoid haemorrhage: Bleeding into the subarachnoid space (the space between the arachnoid membrane and the pia mater of the brain or spinal cord).

Definition of stroke caused by subarachnoid haemorrhage: Rapidly developing signs of neurological dysfunction and/or headache because of bleeding into the subarachnoid space (the space between the arachnoid membrane and the pia mater of the brain or spinal cord), which is not caused by trauma.

Definition of stroke caused by cerebral venous thrombosis: Infarction or haemorrhage in the brain, spinal cord, or retina because of thrombosis of a cerebral venous structure. Symptoms or signs caused by reversible edema without infarction or haemorrhage do not qualify as stroke.

Definition of stroke, not otherwise specified: An episode of acute neurological dysfunction presumed to be caused by ischemia or haemorrhage, persisting ≥ 24 hours or until death, but without sufficient evidence to be classified as one of the above.

Definition of a Transient Ischemic Attack: The definition of Transient Ischemic Attack is according to the American Heart Association/American Stroke Association. Accordingly: a Transient ischemic attack (TIA) is a transient episode of neurological dysfunction caused by focal brain, spinal cord, or retinal ischemia, without acute infarction²⁷.

E) Definition of deep vein thrombosis:

The “Clinical Practice Guideline from the American Academy of Family Physicians and the American College of Physicians” on diagnosis of venous thromboembolism recommends ultrasound scanning for patients with intermediate or high pre-test probability of deep vein thrombosis (DVT) in the lower extremities²⁵. Accordingly, venous thrombosis should be demonstrated by compression ultrasound, duplex ultrasound, colour Doppler imaging or venography (phlebography).

F) Definition of other clinically significant thromboembolic events:

Signs or suspicion of a clinically significant thromboembolic event (e.g. visceral arterial embolus/thrombus, extremity arterial embolus/thrombus, or portal venous thrombosis). Superficial thrombophlebitis is not considered a clinically significant thromboembolic event unless evaluated as such by the investigator.

Protocol
 Trial ID: NN7415-4255
 UTN: U1111-1179-3872
 EudraCT no.: 2016-000614-29

~~CONFIDENTIAL~~

Date:	28 December 2017	Novo Nordisk
Version:	4.0	
Status:	Final	
Page:	86 of 124	

G) Definition of peripheral artery occlusion:

Clinical signs of acute arterial occlusion verified by ankle-brachial index (ABI) test, Doppler and ultrasound (Duplex) imaging, computerised tomographic angiography, magnetic resonance angiogram (MRA), or conventional angiography. The 2011 American College of Cardiology Foundation/American Heart Association Focused Update of the Guideline for the Management of Patients With Peripheral Artery Disease could serve as a reference for the diagnosis of lower extremity peripheral artery disease²⁸

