Table 8–2 Definitions of bleeding episodes (cause of bleed)

Category	Definition
Spontaneous	Not linked to a specific, known action or event
Traumatic	Caused by a specific, known action or event (e.g. injury or exercise)
Post-surgical	Bleeding episodes after surgery from the surgical wound. Bleeding episodes during surgery does not fall under this category

Table 8–3 Definition of bleeding episode severity and treatment recommendation

Category	Definition	Treatment recommendation
Mild/Moderate	Examples: uncomplicated musculoskeletal bleeding episodes (joint, muscular bleeds without compartment syndrome), mucosal- or subcutaneous bleeding episodes Mild/moderate bleeding episodes may occur in other anatomical locations	Mild/moderate bleeding episodes can be treated at home before contact to the investigator
Severe	Examples: intracranial, retroperitoneal, iliopsoas and internal neck bleeding episodes; muscle bleeding episodes with compartment	Severe bleeding episodes must be treated immediately

Protocol
 Trial ID:NN7415-4255
 UTN:U1111-1179-3872
 EudraCT no.:2016-000614-29

~~CONFIDENTIAL~~

Date: 28 December 2017
 Version: 4.0
 Status: Final
 Page: 57 of 124

Novo Nordisk

	
syndrome; bleeding episodes associated with a significant decrease in the haemoglobin level (>3g/dl)
 
Severe bleeding episodes may occur in other anatomical locations
 
Bleeding episodes that require hospitalisation
 
All life-threatening bleeding episodes
	
Instruction for patients	The patient must be instructed to contact the investigator immediately if in doubt regarding treatment of a bleeding episode and to discuss what other actions may need to be taken	

Information about bleeding episodes prior to visit 2 will be recorded in eCRF.

The trial site should be informed of the details of all bleeding episodes, including those that are treated outside of the trial site. After visit 2 bleeding episodes must be recorded either in the eDiary (if treated at home) or in the eCRF (if treated at the trial site), see section [12.3](#).

Severity of bleeding episodes must be evaluated by the investigator according to [Table 8–3](#) and reported in the eDiary database.

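### Section 12.1.6 files primary brain haemorrhage under its only AESI category, thromboembolic events

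*Protocol*

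**What the plan says.** Section 12.1.6 gives a single top-level AESI item, "Thromboembolic events including but not limited to", with sub-items A to G beneath it. Sub-item D is stroke, listed without restriction. The text of D opens as a definition of central nervous infarction, but then says that the term stroke "should be broadly used to include all of the following".

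The list under D includes:

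- "Definition of intracerebral haemorrhage: A focal collection of blood within the brain parenchyma or ventricular system that is not caused by trauma"
- "Definition of subarachnoid haemorrhage: Bleeding into the subarachnoid space"
- silent cerebral haemorrhage, and the clinical strokes caused by intracerebral and subarachnoid bleeding.

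The same list covers bleeding that arises from clotting: "Note: CNS infarction includes haemorrhagic infarctions, types I and II", and stroke from cerebral venous thrombosis is "Infarction or haemorrhage in the brain, spinal cord, or retina because of thrombosis of a cerebral venous structure".

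Elsewhere, Table 8-3 in section 8.3.1 defines severe bleeding episodes with "Examples: intracranial, retroperitoneal, iliopsoas and internal neck bleeding episodes". Section 12.1.1 keeps bleeding episodes out of adverse event reporting unless they are fatal, life-threatening, or attributed by the investigator to trial product or procedure.

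**The concern.** The trial population has severe haemophilia A, so a spontaneous intracranial bleed is an outcome of the disease and may reflect insufficient prophylaxis. Thromboembolism is the opposite kind of event, and it is the potential risk that section 18.1 (version 3) draws from the toxicity studies. As written, 12.1.6 puts both under the thromboembolic heading. A reader of the AESI cases could take a failure to prevent bleeding for a clotting signal.

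The protocol also gives dosing instructions that differ according to how the event is read. Section 8.3.1 has concizumab continue through bleeding episodes unless the investigator judges otherwise. Section 6.4 item 5 makes a thromboembolic event a mandatory reason to stop, and 8.1.4 turns permanent discontinuation into withdrawal from the trial. Item 5 carries no definition, and 12.1.6 is the only section that spells out which events are thromboembolic.

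**Working it through.** No arithmetic applies. The check is to trace the text and see whether anything takes a primary bleed back out of the category.

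**Step 1: does the bleed become an adverse event?** Under 12.1.1, yes, if it is fatal, life-threatening, or judged related to trial product or procedure. Otherwise it stays a bleeding episode only, and 12.1.6 is not reached.

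**Step 2: is it stroke under D?** The entries under D, sorted by what each one requires:

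| Entry in D | Thrombus, infarct or ischaemia required? |
|---|---|
| CNS infarction | Yes; haemorrhagic infarction is included |
| Ischaemic stroke | Yes |
| Silent CNS infarction | Yes |
| Intracerebral haemorrhage | No; trauma is excluded |
| Stroke caused by intracerebral haemorrhage | No; trauma is excluded |
| Silent cerebral haemorrhage | No; trauma is excluded |
| Subarachnoid haemorrhage | No; the base definition has no trauma exclusion |
| Stroke caused by subarachnoid haemorrhage | No; trauma is excluded |
| Stroke from cerebral venous thrombosis | Yes; haemorrhage is included |
| Stroke not otherwise specified | Undetermined: ischaemia or haemorrhage |
| Transient ischaemic attack | Yes (ischaemia without infarction) |

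Five of the eleven entries can be met by a bleed with no thrombotic cause.

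**Step 3: is there an exemption?** The only carve-out in 12.1.6 is for superficial thrombophlebitis, in F. None concerns haemorrhage. Version 3 of the section reads the same.

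**Step 4: are the haemorrhage entries needed to catch thrombotic bleeding?** Largely not. Haemorrhagic infarction and haemorrhage from cerebral venous thrombosis have their own entries. The exception is a note inside the intracerebral entry: "Note: Intracerebral haemorrhage includes parenchymal haemorrhages after CNS infarction, types I and II". That entry therefore mixes post-infarct bleeds with primary ones, and any rewording must keep the post-infarct bleeds on the thromboembolic side.

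**Step 5: what changes because of the label?**

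- *Capture.* 12.1.1 sends all bleeding episodes to the eCRF or eDiary in any case.
- *Forms.* 12.2 requires an adverse event form and a safety information form for serious events and for AESIs alike. A fatal or life-threatening bleed is already serious.
- *Endpoints.* Bleeding endpoints count treated bleeds (section 17, version 3). Adverse events are summarised by MedDRA class and term, seriousness, severity and relation (17.6.2, version 3). No endpoint uses the AESI category, and no AESI count or proportion is planned there.
- *Stopping and hold rules.* 6.4 lists a thromboembolic event and DIC as separate items, and 12.7 (version 3; the version 4 section is not in the text at hand) does the same. In 12.1.6, DIC sits inside the thromboembolic category. Neither 6.4 nor 12.7 refers to 12.1.6. This suggests that those rules do not simply import the 12.1.6 list. On the other side, the footnote to 12.7 echoes the superficial thrombophlebitis carve-out in F, and 6.4 item 5 is left undefined. The text does not settle the matter.

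**The case against.** The best defence is that the category is a deliberately broad net for coagulation safety. It is open-ended, its first sub-item (DIC) may be diagnosed on a bleeding tendency as well as a thrombotic one, and section 18.1 (version 3) names bleeding from consumption of coagulation factors as a theoretical risk. Over-inclusion is the cautious direction. A broad entry also spares the investigator a decision on cause when evidence is thin, which the entry for stroke not otherwise specified shows the protocol expects. Table 8-3 is no contradiction either: it sets severity and treatment, and 12.1.1 allows a bleed to be an adverse event as well.

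Much of this stands. Dual capture is legitimate, and close watch on brain bleeds is sensible for this drug. It does not justify the heading, because the same watch can be kept under an accurate one. The point about uncertain cause is met by leaving undetermined cases in the thromboembolic group.

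A reader might go further and infer that a brain bleed would force discontinuation under 6.4 or halt enrolment under 12.7. The documents do not support that: both rules list DIC separately, neither cites 12.1.6, and 12.7 leads to a safety committee meeting while dosing may continue. Nor is a distorted thromboembolic rate shown, since no such rate is specified and no expected number of brain bleeds is given.

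**Conclusion.** The classification rule is wrong as written: a primary brain haemorrhage that meets the 12.1.1 condition is by definition a thromboembolic AESI. The size is minor. What remains is a misleading entry in the category that tracks the drug's main named potential risk, and an open question about whether 6.4 item 5 covers such a bleed. The conclusion on classification rests only on the wording of 12.1.6 and 12.1.1. The statement that endpoints and planned summaries are unaffected rests on the version 3 text of section 17. No event rate is assumed or claimed.

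**What to change.** In 12.1.6, restrict the thromboembolic category to:

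- CNS infarction, including haemorrhagic infarction and parenchymal haemorrhage after infarction;
- ischaemic stroke and silent CNS infarction;
- stroke from cerebral venous thrombosis;
- transient ischaemic attack;
- stroke not otherwise specified or of undetermined cause.

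Keep primary haemorrhagic CNS events as a separate AESI category with the same forms and timelines. Add one sentence to 6.4 saying whether a primary brain haemorrhage is a thromboembolic event for mandatory discontinuation. Any stop rule specific to brain bleeds is for the sponsor's medical team to write.

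The cost is one extra AESI category and the need for the investigator to assign a cause, with undetermined cases staying in the thromboembolic group. No new data or visits are needed, and no safety capture is lost.
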